## **Obstructive Sleep Apnea in WTC responders: Role of nasal Pathology**

**Title of Project:**

**Principal Investigator:**

**[name]**

**Funding Source(s):**

**Centers for Disease Control/ NIOSH**

### **1. Purpose/Specific Aims**

Following the World Trade Center (WTC) disaster, responders who worked in rescue, recovery and debris removal were initially exposed to greater than 100,000  $\mu\text{m}^3$  total particles. 63% of these responders examined in 2004 reported at least one new or worsened upper airway respiratory symptom since 9/11, and in June 2007, 50% of responders continued to have symptoms of chronic rhino-sinusitis or upper airway disease (UAD). In addition, about 50% of those with UAD referred to our sleep center reported new onset snoring on their questionnaires immediately following their exposure and had unusually high prevalence of obstructive sleep apnea (OSA). Usual risk factors for OSA include a high body mass index (BMI) and increasing severity of OSA as determined by the apnea+hypopnea index (AHI) correlates with increasing BMI. Unique to the WTC population was the fact that there was no correlation between AHI and BMI and those with new onset snoring had a lower BMI compared to habitual snorers. This suggests that mechanisms other than obesity may be important in the pathogenesis of OSA in these subjects and given their chronic nasal symptoms, provides a unique opportunity to examine the relationship between nasal pathology and OSA. Our hypothesis is that the nasal symptoms reported by the subjects in the WTC medical monitoring and treatment program (WTCMMTP) now termed WTC Health Program (WTCHP) are an indicator of increased nasal resistance due to nasal inflammation resulting from exposure to the WTC dust. In particular reversible nasal resistance may play an important role. Alternatively inflammation of the posterior pharynx without influencing nasal resistance may predispose to OSA in this population. Continuous Positive Airway Pressure (CPAP) is the standard therapy for OSA but despite its efficacy has poor adherence. Subjects with high nasal resistance may experience additional pressure during expiration at the upper airway due to high nasal resistance. This may result in greater difficulty in tolerating this therapy than those who do not have high nasal resistance. Reduction of excess expiratory positive pressure by the modality known as Cflex™ during CPAP therapy (CPAPFlex) has been suggested to improve comfort without compromising CPAP efficacy.

**SA3. Relate nasal resistance to CPAP adherence in patients with OSA and show that reduction of expiratory pressure using CPAPFlex will improve CPAP adherence.** Patients with OSA will be randomized in a double blind cross over design to receive CPAP or CPAPFlex and adherence will be measured.

*In patients with OSA, we will test:*

*Hypothesis 3a: Increased nasal resistance is associated with decreased adherence to CPAP.*

*Hypothesis 3b: Use of CPAPFlex will improve adherence with CPAP in subjects with high nasal resistance, but not in those with low nasal resistance.*

*Hypothesis 3c: The benefit of CPAPFlex on adherence will be greatest if it is offered at CPAP initiation rather than as a “rescue” therapy in subjects with high nasal resistance.*

[figure not shown]
## **2. Background and Significance**

From September 11, 2001 onward following the World Trade Center (WTC) disaster, an estimated 40,000 individuals were exposed to significant amounts of dust while working in rescue, recovery and debris removal. These workers included traditional first responders, such as firefighters and police, and a diverse population of construction, utility, and public sector workers. A medical screening program was developed to evaluate the health status of workers and volunteers who spent time at the WTC site and thus sustained exposure in the aftermath of September 11th. Standardized questionnaires were adapted for use in this unique population. These questionnaires underpin our exploration of the relationship between the new symptoms following the exposure and the presence of diseases such as OSA. The WTC Worker and Volunteer Medical Screening Program (MSP) and the follow up World Trade Center Medical Monitoring and Treatment program (WTCMMP) now called the World Trade Center Health program (WTCHP) have successfully recruited more than 27,000 responders to assess and treat health effects from these exposures. About 1700 of these responders are followed at the Environmental and Occupational Health Sciences Institute (EOHSI) of Rutgers Biomedical Health Sciences in Piscataway, New Jersey, about 2100 in the NYU School of Medicine Clinical Center of Excellence (NYUSOM CCE) at Bellevue Hospital in New York City and about 22,000 are followed at Mt. Sinai School of Medicine (MSSM CCE).

[figure not shown]
## Obstructive Sleep Apnea in WTC responders: Role of nasal Pathology

[name]

The collapse of the WTC towers resulted in a massive plume of building debris and particulates. Sources of associated pollutants varied over the months after the disaster, but included combustion products, evaporating gases, gaseous fine and supercoarse particles. These were from dust, rubble and debris from breakdown of WTC buildings, gases, dust, soot and smoke formed as a result of fires at the WTC site and motor vehicle emissions from vehicles at the WTC site. The dust was highly alkaline and corrosive, capable of causing chemical irritation to the upper respiratory tract. It contained high levels of calcium sulfate (gypsum) and calcium carbonate (calcite) known causes of irritation to mucus membranes (eyes, nose throat and large airways) as well as cough and sneezing and are likely to be among the major irritants of WTC dust.

OSA is a chronic condition with recurrent episodes of partial or complete upper airway collapse during sleep. The main risk factors for OSA are obesity and male gender and it is highly prevalent in the general population, with estimates ranging from 5-10% to >25%. Upper airway inflammation resulting in mucosal congestion could mimic these predisposing conditions and provide an alternate mechanism for development of compromised upper airway patency during sleep.

[Redacted]

[Redacted]

[Redacted]

[Redacted]

The health benefits of diagnosis and treatment of OSA are well recognized: untreated OSA is associated with daytime sleepiness, increase in motor vehicle accidents, increased hypertension, stroke, impaired glucose metabolism, and increase in all-cause mortality. CPAP is the primary treatment for OSA. CPAP use normalizes sleep architecture, reduces daytime sleepiness, and reduces automobile accidents and decreases blood hypertension and cardiovascular events. Despite its efficacy, 29-83% of patients are non-adherent to CPAP and no specific factors (demographic, disease specific) that predict CPAP adherence have been identified. In addition to problems with the mask and claustrophobia, pressure intolerance and “difficulty exhaling” are frequently cited by patients as limiting acceptance of CPAP therapy. Nasal symptoms and side effects are also common and may account for 30-50% of cases of CPAP intolerance. Thus, in addition to its role in causing OSA, elevated nasal resistance may impact on initial acceptance of CPAP. Small studies have shown that nasal resistance was significantly higher in OSA patients who did not tolerate CPAP and reduction of nasal resistance by surgery has been shown to increase CPAP use. CPAP adherence in WTC responders with UAD is unknown but in general has anecdotally been thought to be poor. High nasal resistance can play a potential role in their poor adherence.

CPAP keeps the UA open and nasal resistance becomes the primary determinant of total UA resistance. Thus, during CPAP use, high nasal resistance may continue to cause a patient to experience discomfort while exhaling despite adequate relief of OSA and could contribute to intolerance of CPAP. In preliminary data we have shown that, as expected, increased nasal resistance results in higher expiratory pressure. By decreasing this excess pressure during the expiratory cycle, CPAPFlex (Philips Respironics) may improve CPAP adherence. Although prospective, randomized studies have demonstrated that CPAPFlex is not inferior to conventional fixed CPAP, increased adherence has not been uniformly demonstrated. Some studies have shown CPAPFlex reduces discomfort and improves adherence, but larger randomized studies have shown no difference in adherence between CPAP and CPAPFlex. However none of these studies have attempted to target therapy to patients based on elevated nasal resistance as we propose to do. **In specific aim 3 of this proposal we will relate nasal resistance to CPAP adherence in patients with OSA and show that reduction of expiratory pressure using CPAPFlex will improve CPAP adherence.**

[Redacted]

[Redacted]

[Redacted]

[Redacted]

[Redacted]

### 3. Research Design and Methods

[REDACTED]

[REDACTED]

[REDACTED]

[REDACTED]

[REDACTED]

[REDACTED]

[REDACTED]

Objective Assessment of nasal pathology:

Clinical Examination: An investigator (a study physician, a research assistant, or the research coordinator) will perform a visual inspection of the inside of the nose to identify redness, swelling, polyps or polypoid swelling, crusting, mucus, and or frank pus. An oral exam will also be done to evaluate characteristics of the mouth (including tongue position, tonsillar size, and uvula size and a score will be given for each [name] will train all study investigators to perform the visual exams.

Rhinomanometry: The study technician will perform rhinomanometry which is a measurement of airflow through the nose. We will assess nasal resistance using the 4-phase-rhinomanometer (RhinoLab GmbH, Rendsburg, Germany) following the detailed technical, practical methodology, and referenced normative data published in the literature. Briefly, during the rhinomanometry procedure, a small tube is held in place using tape over one nostril and a mask is placed on the subject's nose. The subject will be asked to take a few breaths with his/her mouth closed. The procedure will be repeated with the other nostril. Initially, the subject will be seated during measurement and measurements will be performed twice, before and 10 minutes after decongestion with 0.05% Xylometazoline solution. The procedure will be repeated while the subject is lying down. We have previously collected data using active anterior rhinomanometry (RhinoStream, Rhinometrics A/S, Lyngø, Denmark) and published supine and sitting nasal resistances in subjects in patients coming to NYU sleep laboratory. For the present study, we will change to the newer technology to bring it into accord with the more recent standardization recommendations.

Home monitoring for OSA: Subjects will be given an ARES™ Unicorder (pictured) or a similar device (such as Embletta) and a separate wrist pulse oximeter (Nonin WristOx2 Model 3150) to take home and wear for 2 nights, with a pre-addressed mailer to return the devices to the sleep lab. The ARES Unicorder is routinely used in clinical practice for home monitoring of OSA. The ARES Unicorder is worn on the forehead and does not require additional wires to external devices. It measures oxygen saturation and pulse rate from reflectance oximetry, airflow from a nasal cannula/pressure transducer, snoring via acoustic microphone and head movement actigraphy and head position from accelerometers. The device also provides audible alerts during the study if poor quality airflow or SpO2 is detected so the subject can reposition the device. The wrist pulse oximeter

will be used to correct for the drift in oxygen saturation found in previous studies with the ARES™ Unicorder.

Analysis of Respiratory Data from ARES: Data from the monitor will be autoscored and then manually reviewed by a single trained sleep technician at NYU SOM. Data from ARES will be de-identified; only the study ID will be used in monitoring. Apneas will be scored when there is a reduction in airflow to less than 10% of baseline. We have extensive experience using the ARES device and have validated it against NPSG (Nocturnal Polysomnography) in over 300 subjects in multiple research studies.

**SA3. Relate nasal resistance to CPAP adherence in patients with OSA and show that reduction of expiratory pressure using Cflex will improve CPAP adherence. Patients with OSA will be randomized in a double blind cross over design to receive CPAP or CPAPFlex and adherence will be measured as average hours of use over 2 weeks.**

**Protocol for SA3** 1. From the ARES studies, we expect to identify ~500 subjects with OSA. We expect about 10% to refuse to even try CPAP. All others would be recruited to be randomly assigned to CPAP or CPAPFlex as a first treatment, and crossed over to the other after completing the first arm of the protocol.

2. Initially, the subject will be treated using the AutoCPAP program which varies the pressure, generally between 5 and 15 cm water, depending on the obstruction. If used regularly (for at least 4 hours a night for 2 nights), a fixed pressure will be automatically assigned. If the subject does not regularly use CPAP, treatment will continue using the autotitrate program. The technician will monitor CPAP treatment to ensure adequate treatment when the subject uses CPAP. The automated AHI is monitored to ensure efficacy of therapy (AHI of <10 events per hour of sleep). If the AHI is >10 events per hour of sleep the data is reviewed by a designated sleep physician and the pressure is modified or the patient is recommended for an in laboratory sleep study if indicated.

3. Adherence monitoring will be made from the CPAP machine for 1 month with first intervention, then switched to the alternate intervention and adherence monitored for another month. Data from last 2 weeks of each period will be used for objective adherence comparisons between interventions. Periods of reported non-use by the subject due to illness or travel will not be included in the treatment periods. The trial periods may be extended for up to 1 month due to instrument (CPAP machine or modem) failure. Instrument failure is not expected to exceed 10% of the users. At the end of the trial, subjects will be asked to return the modem either by mail or in person. If the subject returns the modem in person, he/she will be asked to repeat the nasal lavage sample. The subject will be informed that the purpose of this sample is to collect preliminary data. The pre-CPAP and post-CPAP samples will be compared to determine if CPAP use has any effect on markers in the lavage sample.

4. Subjective assessment of sleepiness, quality of life and satisfaction with therapy will be obtained using questionnaires administered at the start and end of each period.

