### **Procedures for SA3**

Initiation of Therapy: Within 6 months of the home monitoring identify OSA, subjects will return to the clinic for CPAP therapy and will undergo mask fitting and desensitization and CPAP education during this visit. CPAP education will follow a written protocol common to both sites. During the first two weeks of therapy, the research co-coordinator will call the patients each week to discuss any mask or CPAP related issues. If the subject experiences any problems, he/she may

return to the clinic for additional support or mask replacement. If more than 6 months elapse after the home monitoring and the subject wishes to participate in the CPAP trial, the subject will be asked to repeat the initial assessment including questionnaires, rhinomanometry, nasal lavage, and home sleep testing.

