### **3.5.4 Consent Procedures**

**Clinic Recruitment:** If the subject has asked to be contacted about the study (placed a contact card in the clinic box), a study investigator (research assistant, research coordinator) will call the subject and read the study screening script for clinic contacts.

**Mail Recruitment:** If the subject has been recruited by mailing, a member of the clinic staff will call the subject and read the study screening script for DCC contacts.

After reading the script (either for clinic contacts or DCC contacts), if the subject is interested in participating, their contact information will be recorded, a copy of the consent form will be mailed, and an appointment will be made for the first clinic visit. The subject will be called the preceding workday to confirm the appointment. The subject will be asked if he/she is experiencing seasonal allergies or had a recent cold. If yes, the appointment will be re-scheduled so that all symptoms have subsided at least 2 weeks prior to the appointment.

**Clinic contacts only:** If the subject is in the clinic and requests information about the study, the screening may be done in-person, in a private office. If eligible, the subject will be given a consent form to read. After reading it, the investigator will review the study and answer any questions. The consent form will be signed by the subject and the investigator. The subject will be given a copy of the signed document. An appointment will be made for the clinical visit.

If the subject wishes to think about participating, he/she will be given a copy of the consent form to take home. The investigator will record contact information and contact the subject in a few days. If the subject wishes to participate, an appointment will be made for the clinic visit. Consent will be obtained on the day of the clinic visit as outlined below.

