### **Consent Signature**

**Clinic and DCC contacts:** Subjects may return the signed consent form by mail. Once the consent form is received, an investigator will call the subject, answer any questions, and confirm participation. These subjects may then do the home sleep monitoring prior to their first clinic visit.

The monitor will be mailed with a signed copy of the consent form. If the clinic visit is scheduled first, on the day of the clinic visit, the consent form will be reviewed with the subject by a member of the study team. All questions will be answered. If the subject wishes to enroll, he/she will be asked to sign and date the consent form. The study investigator will also sign and date the consent form. The subject will be given a copy of the signed document.

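### The before/after-CPAP nasal lavage comparison pairs a symptom-deferred baseline with an end sample that has no stated symptom condition, time window or untreated comparison, so any change should not be reported as an effect of CPAP

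*Protocol*

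**What the plan says.** **End sample.** Protocol section 3, Protocol for SA3, item 3, gives two routes for returning the modem: "At the end of the trial, subjects will be asked to return the modem either by mail or in person". Only one leads to a sample: "If the subject returns the modem in person, he/she will be asked to repeat the nasal lavage sample". The purpose follows: "The pre-CPAP and post-CPAP samples will be compared to determine if CPAP use has any effect on markers in the lavage sample". The same item has subjects told that the sample is for preliminary data.

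**Baseline sample.** Procedures for SA3 (Initiation of Therapy) shows that lavage belongs to the initial assessment. Subjects who want to start CPAP more than 6 months after home monitoring must "repeat the initial assessment including questionnaires, rhinomanometry, nasal lavage, and home sleep testing". Section 3.5.4 describes the call confirming the first clinic visit: "The subject will be asked if he/she is experiencing seasonal allergies or had a recent cold". The consequence is: "If yes, the appointment will be re-scheduled so that all symptoms have subsided at least 2 weeks prior to the appointment".

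**Timing.** CPAP need not start soon after diagnosis: "Within 6 months of the home monitoring identify OSA, subjects will return to the clinic for CPAP therapy". Two one-month treatment periods follow. Home monitoring can come before the first visit for subjects who mail back their consent (Consent Signature): "These subjects may then do the home sleep monitoring prior to their first clinic visit". The baseline lavage therefore has no fixed date relative to home monitoring.

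**Analysis.** The SAP covers adherence (primary) and AHI on treatment (secondary). It gives no analysis for the lavage markers.

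**The concern.** The plan treats a recent cold or seasonal allergy as reason enough to postpone the visit belonging to the initial assessment. It states no matching precaution for the end sample. Where the baseline rule is applied, a subject starts free of those symptoms and can only stay so or become symptomatic by the end. If symptoms move a marker in a consistent direction, that part of the change is systematic, and a larger sample does not remove it. Season and elapsed time add a second source of change, of unknown direction.

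Randomisation does not protect this contrast. It allocates the order of CPAP and CPAPFlex, and every subject is assigned to both. A before/after comparison within these subjects has no concurrent group that passed through the same months without CPAP.

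At stake is the reading of an exploratory result. The trial's hypothesis concerns nasal inflammation after dust exposure. A rise produced by colds or pollen could be taken as CPAP irritating the nose, or could mask a true fall, and preliminary data of this kind tend to shape later studies.

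**Working it through.** The documents give no sample size, SD or effect size for the lavage comparison, so there is no plan figure to reproduce. The check sets the conditions of the two samples side by side, sums the intervals and adds an illustration.

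**1. Conditions of the two samples (visible text)**

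| | Baseline lavage | End lavage |
|---|---|---|
| Who | Part of the initial assessment | Only those returning the modem in person |
| Cold/allergy question | At the call confirming the first visit | None stated |
| Deferral | 2 weeks symptom-free | None stated |
| Time window | Initial assessment repeated if more than 6 months pass after home monitoring | None stated |
| Untreated comparison | – | None described |

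Item 3 leaves reported non-use through illness or travel out of the treatment periods. That rule governs which nights count for adherence; it is not a condition on the day of the lavage.

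**2. Elapsed time, in months**

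- Lavage close to CPAP start: 0 + 1 + 1 = 2.
- Lavage at home monitoring, CPAP started 6 months later: 6 + 1 + 1 = 8.
- Adding the instrument-failure extension (up to 1 month) and two contact extensions of about 2 weeks (Subjective Assessment): 8 + 1 + 2 × 0.5 = 10.
- The same, if the instrument extension applies to each period (the text does not say): 8 + 2 + 2 × 0.5 = 11.

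A lavage taken before home monitoring, or time excluded for illness or travel, would lengthen these figures. The gap can cross allergy seasons. How often it does is not derivable, because the documents give limits and no distribution.

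**3. Illustration with no true CPAP effect (assumed inputs)**

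Let q be the share of end samples taken while symptomatic, d the marker shift in SD, and ρ the correlation between a subject's two samples. With a symptom-free baseline:

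- apparent mean change = q × d
- variance of the paired difference = 2(1 − ρ) + d²q(1 − q)
- false rejection = chance that a two-sided 5% paired z-test rejects

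From the protocol: about 500 subjects with OSA, 10% refusing, so 500 × 0.90 = 450. Assumed: ρ = 0.5 and 25% returning in person, so n = 450 × 0.25 = 112.5.

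| q | d | Apparent change (SD) | False rejection |
|---|---|---|---|
| 5% | 0.5 | 0.025 | 5.8% |
| 10% | 0.5 | 0.05 | 8.2% |
| 10% | 1.0 | 0.10 | 17.4% |
| 20% | 1.0 | 0.20 | 50.4% |
| 30% | 1.0 | 0.30 | 82.5% |

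For the third row, the variance is 1 + 0.10 × 0.90 = 1.09, the standard error is √(1.09/112.5) = 0.098, and the mean change is 0.10/0.098 ≈ 1.02 standard errors.

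Over the whole assumed range (10–50% returning in person, so n = 45 to 225; q = 5–30%; d = 0.5–1.0) the apparent change is 0.025 to 0.30 SD and false rejection runs from 5% to 98%. If a share q₀ is symptomatic at baseline too, the apparent change shrinks to (q − q₀) × d; for example (0.20 − 0.05) × 1.0 = 0.15 SD.

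**The case against.** The strongest reply is that much of the relevant text cannot be seen. Section 3 opens with redacted blocks, and no visible text says how lavage is collected, which markers are assayed or how they are analysed. A symptom check at the end sample could sit there. This stands: the point can only be that no condition is stated in the visible text.

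Several stronger readings are tempting, and the documents do not support them.

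- A reader might infer that the analysis is a simple mean difference, or that subjects who hardly used CPAP are counted as treated. Neither is stated. The text says only that the samples will be compared, the question is put in terms of CPAP use, and nightly use is recorded. A usage-based analysis is compatible with it.
- A reader might infer that every baseline is symptom-free. The question belongs to the confirmation call for the first visit. It is not expressly repeated for subjects screened in the clinic or for the repeat assessment after 6 months, and it covers only colds and seasonal allergy, in a population with much chronic upper-airway disease. A less uniform screen shrinks the asymmetry.
- A reader might infer an upward bias in inflammation. The text says markers and names none, so the direction depends on the marker.
- A reader might infer that self-selection through the return route biases the change. It mainly limits representativeness. It biases a within-subject change only if the choice of route relates to symptoms, CPAP experience or marker change.

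The rule to repeat the assessment after 6 months is a genuine partial safeguard: it refreshes an old baseline. It does not align the end sample's symptom conditions or supply a comparison group.

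Finally, the sample is preliminary and supports none of hypotheses 3a to 3c. That limits the importance of the point but does not remove it, since the protocol still states a causal aim.

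**Conclusion.** The point holds as a minor design and reporting weakness. In the visible text the two lavage samples are taken under different symptom conditions, the end sample has no time window, and no untreated comparison is described. The comparison as described cannot separate CPAP from intercurrent symptoms, season or elapsed time.

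The gap of about 2 to 8 months, or 10 to 11 with extensions, follows from stated intervals, taking the lavage to fall between home monitoring and CPAP start. The 0.025 to 0.30 SD and the false-rejection rates do not: they rest on assumed symptom frequency, marker shift, correlation and in-person return, and on a symptom-free baseline. They show that the mechanism could matter, not that it will. The conclusion also assumes that redacted text contains no matching condition for the end sample. The primary and secondary outcomes are unaffected.

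**What to change.** 1. When the in-person modem return is arranged, ask the cold and seasonal-allergy question from section 3.5.4. Either apply the same two-week condition, or take the sample, flag it and exclude it from the main lavage comparison.
2. Record the dates of both samples.
3. Report the result as an uncontrolled pre/post change, and reword the stated purpose so that it does not promise an effect of CPAP.
4. Optionally, add a supportive regression of marker change on recorded CPAP hours, adjusted for baseline nasal resistance and the calendar timing of the samples. Describe it only as an association. Hypothesis 3a expects use to depend on nasal resistance, so low users are not a clean stand-in for untreated subjects.

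If redacted text already sets an end-sample condition, item 1 needs only a cross-reference.

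The cost is one question, some later modem returns, two dates on a form and, if wanted, one regression on data already collected. The downside is slightly fewer usable end samples.
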